7.2.2. Exclusion Criteria

A patient will be excluded from this study if any of the following criteria are met:

1. History and/or current evidence of clinically significant non-tumor related alteration of calcium-phosphorus homeostasis.

2. History and/or current evidence of clinically significant ectopic mineralization/calcification.
3. History and/or current evidence of clinically significant retinal disorder confirmed by retinal examination.
4. History or current evidence of serious uncontrolled ventricular arrhythmias
5. Fridericia's corrected QT interval (QTcF) > 470 ms on ECG conducted during Screening.
6. Treatment with any of the following within the specified time frame prior to the first dose of TAS-120:
 - a. Major surgery within the previous 4 weeks (the surgical incision should be fully healed prior to the first dose of TAS-120).
 - b. Radiotherapy for extended field within 4 weeks or limited field radiotherapy within 2 weeks.
 - c. Patients with locoregional therapy, e.g., transarterial chemoembolization (TACE), selective internal radiotherapy (SIRT) or ablation within 4 weeks.
 - d. Any noninvestigational anticancer therapy within 3 weeks or have not recovered from side effects of such therapy prior to TAS-120 administration (mitomycin within prior 5 weeks).
 - Targeted therapy or immunotherapy within 3 weeks or within 5 half-lives (whichever is shorter)
 - e. Any investigational agent received within 5 half-lives of the drug or 4 weeks, whichever is shorter. Concurrent participation in an observational study may be allowed after review by the Sponsor's Medical Monitor.
 - f. Patients with prior FGFR-directed therapy.
7. A serious illness or medical condition(s) including, but not limited to, the following:
 - a. Known brain metastasis (not including primary brain tumors) unless patient is clinically stable for ≥ 1 month.
 - b. Known acute systemic infection.
 - c. Myocardial infarction, severe/unstable angina, symptomatic congestive heart failure (New York Heart Association [NYHA] Class III or IV (see [Appendix D](#), New York Heart Association [NYHA] Classification) within the previous 2 months; if > 2 months, cardiac function must be within normal limits and the patient must be free of cardiac-related symptoms.
 - d. Chronic nausea, vomiting, or diarrhea considered to be clinically significant in the opinion of the investigator.
 - e. Congenital long QT syndrome, or any known history of torsade de pointes, or family history of unexplained sudden death.
 - f. Other severe acute or chronic medical or psychiatric condition or laboratory abnormality that in the judgment of the investigator would make the patient inappropriate for entry into this study.
8. Patients with a history of another primary malignancy that is currently clinically significant, and has potential for metastases or currently requires active intervention (except for gonadotropin-releasing hormone (GnRH) or luteinizing hormone-releasing

hormone (LH-RH) agonists in prostate cancer or adjuvant hormonal therapy in breast cancer).

9. Pregnant or lactating female.

7.3. Discontinuation Criteria

A patient is considered discontinued from study treatment when the decision to permanently stop TAS-120 is made. Any TAS-120 discontinuation should be fully documented.

7.3.1. End of Treatment Discontinuation Criteria

The reason for discontinuation should be documented in the source documents.

Patients can be withdrawn from treatment for the following reasons:

- At the patient's request at any time irrespective of the reason.
- RECIST-defined disease progression of solid tumors or RANO-defined disease progression of brain tumors.
- Clinical progression.
- Unacceptable adverse events (AEs), or change in underlying condition such that the patient can no longer tolerate therapy, as evidenced by:
 - A dose delay > 21 days from the scheduled start date of the next cycle.
 - Need for more than the allowed dose reductions of TAS-120 as described in [Section 8.1.3.1](#), TAS-120 Dose Reductions for Treatment-emergent Toxicities.
- Physician's decision including need for other anticancer therapy not specified in the protocol, or surgery or radiotherapy to the only site(s) of disease being evaluated in this protocol.
- Pregnancy.

Upon discontinuation of treatment the investigator is to ensure the following:

- The Clinical Research Associate (CRA) must be notified immediately; and
- The Study Treatment Discontinuation Form in the electronic case report form (eCRF) must be completed, specifying the primary reason for the patient's withdrawal from the study.

If there is strong evidence of clinical benefit and reasons to justify continuation of TAS-120 dosing even though treatment discontinuation criteria have been met, this decision must be reviewed with the sponsor on a case-by-case basis, and continuation of therapy may be allowed assuming all other treatment resumption criteria have been met. Post-study provisions are provided in [Section 13.4](#).

7.4. Patient Numbering and Treatment Allocation

Study sites will enter patient demographic and screening data into the eCRF in order to receive a patient number.

The eCRF will assign each patient a unique patient number. This patient number will be maintained throughout the study and will not be reassigned. Patients who withdraw consent or discontinue from the study after being assigned a patient number will retain their initial number.

Phase 1 Expansion and Phase 2:

Patients will be registered by interactive voice/web response system (IXRS) into Phase 1 Expansion and Phase 2 parts of the study. The institutional designee will call/login to the IXRS and will enter patient data as outlined in the IXRS Manual. After registration of the enrollment visit, the IXRS will assign TAS-120 by kit number, inform the study site user of the kit numbers that have been assigned to the patient, and provide instructions for the dispensing of TAS-120. Please refer to the IXRS Manual for detailed information.

If a patient is mistakenly given a kit of TAS-120 that is not the correct kit number as assigned by the IXRS, the IXRS help desk must be notified immediately. The reason for the misallocation of the study medication must be documented by the study site.

7.5. Replacement Criteria

No patients will be replaced during the Phase 1 Expansion or Phase 2 parts of the study.

7.6. Prohibited Medications and Therapies

Patients are not permitted to receive any other investigational or any other anticancer therapy, including chemotherapy, immunotherapy, biological response modifiers, or antineoplastic endocrine therapy during the study treatment period.

7.7. Concomitant Medications and Therapies

The following therapies are permitted:

- Bisphosphonate
- Denosumab
- Concomitant treatment with GnRH agonists or LH-RH agonists is permitted in prostate cancer patients.
- Non enzyme-inducing anticonvulsants such as: Gabapentin (Neurontin), Lamotrigine (Lamictal) and Levetiracetam (Keppra).
- Steroids are allowed for patients with primary brain tumors and brain metastases. Steroid use in other patients with other tumor types should be discussed between the investigator and the Sponsor's Medical Monitor.
- Local or regional palliative cryotherapy or radiation, e.g., for bone pain or palliative surgery (non-anti-neoplastic intent).

If, after assessment by the Investigator, radiation for brain metastasis, therapy for bone metastasis, or locoregional therapy e.g. local ablation, TACE, SIRT or arterial infusion chemotherapy should be initiated for the best benefit of the patient, the patient can start such therapy a minimum of 2 days after discontinuation of TAS-120. Consequently, the patient will be

censored for the primary endpoint analysis. TAS-120 may be restarted 2 weeks after completion of such treatment or when the patient has recovered from the side effects of such treatment.

The following medications/therapies may be given concomitantly under the following guidelines:

Hematologic Support

For Phase 1 Expansion and Phase 2, hematologic support may be administered as medically indicated (e.g., blood transfusions, CCI, erythropoietin stimulating agents) according to the institutional site standards. If there are no standard procedures for the use of growth factors, the American Society of Clinical Oncology [ASCO] Guidelines for Use of Hematopoietic Colony-Stimulating Factors, available at www.asco.org, will be followed.

Management of Diarrhea

For Phase 1 Expansion and Phase 2, prophylactic treatment for diarrhea is permitted during the study if clinically indicated according to the institutional guidelines. If there are no institutional standards, refer to the guidelines published by Benson AB, et al in *Journal of Clinical Oncology*.¹⁵

Management of Nausea/Vomiting

Antiemetics may be administered as clinically indicated. If there are no institutional standards, refer to the ASCO Guidelines for Antiemetics in Oncology.¹⁶

Management of Hyperphosphatemia

Phosphate-lowering therapy must be started within 24 hours after observing elevated phosphorus (≥ 5.5 mg/dL [≥ 1.78 mmol/L]). Serum phosphorus is to be tested 4 days (± 24 hours) after Day 1 of Cycle 1 to initiate early intervention for hyperphosphatemia.

Hyperphosphatemia management should follow institutional practice with phosphate binding agents, such as Sevelamer, acetazolamide or Fosrenol, or other phosphate binders or a combination of these agents. Sevelamer (both tablets and powder) should preferably be taken during meals in order to improve gastrointestinal tolerance and compliance. Lanthanum carbonate (Fosrenol) should be taken immediately after meals; tablets may be cut if required for administration. Other phosphate binders and hyperphosphatemia treatment drugs may also be used. In addition, actively managing constipation by drinking water and following dietary guidelines (see [Appendix E](#)) may also decrease the risk of hyperphosphatemia.

Refer to [Section 8.1.3.1.1](#) for details on dose interruption or reduction in the management of hyperphosphatemia.

Drug interactions with TAS-120

Drug interaction studies have not been conducted in humans. The following information is based on results from *in vitro* studies. Caution is advised if these drugs are given concomitantly (see [Appendix F](#), Classification of Substrates, Inhibitors, and Inducers of CYP Enzymes and Transporters).

Cytochrome P450 (CYP) 3A inhibitors and inducers: CYP3A is involved in the metabolism of TAS-120. CYP3A inhibitors and inducers may alter the concentration and activity of TAS-120.

CYP3A substrates: TAS-120 is a potential time-dependent inhibitor of CYP3A. TAS-120 may increase the concentration and activity of CYP3A substrates.

P-glycoprotein (P-gp) and breast cancer resistance protein (BCRP) substrates and inhibitors: TAS-120 is a substrate of P-gp and BCRP, and a potential inhibitor of P-gp and BCRP. TAS-120 may alter the PK and activity of P-gp and BCRP substrates. P-gp and BCRP inhibitors may alter the concentration and activity of TAS-120.

7.7.1. Effective Contraception During Study

Female patients who are considered not to be of childbearing potential must have a history of being postmenopausal (no menses for 12 months without an alternative medical cause), or hysterectomy that is clearly documented in the patient's source documents.

For WOCBP, including female study participants and partners of male participants, effective contraception is required during the trial and for 6 months after the last dose of study medication. Effective contraception is defined as follows:

- combined (estrogen and progestogen containing) hormonal contraception associated with inhibition of ovulation:
 - oral
 - intravaginal
 - transdermal
- progestogen-only hormonal contraception associated with inhibition of ovulation:
 - oral
 - injectable
 - implantable
- intrauterine device (IUD)
- intrauterine hormone-releasing system (IUS)
- bilateral tubal occlusion
- vasectomized partner with documentation of the success of the vasectomy
- complete abstinence from heterosexual intercourse (periodic abstinence is not a safe method)

Male patients with partners who are WOCBP should use a combination of male condom with cap, diaphragm, or sponge with spermicide during the trial and for 6 months after the last dose of study medication.

7.8. Dietary Restrictions

Limitation of phosphate intake including avoidance of foods that are especially high in phosphate, e.g., dairy products, meats, nuts, and other high-protein foods, processed foods, and colas (e.g., Pepsi) is recommended as part of hyperphosphatemia management. Dietary Guidelines for Treatment of Hyperphosphatemia are provided in [Appendix E](#).

8. STUDY DRUG

8.1. Study Drug Administration and Dose Modification Procedures

8.1.1. Study Drug Administration

TAS-120 is supplied as 4 mg tablets. The dose for TAS-120 is 20 mg QD. Patients should follow the instructions of the treating physician on study drug administration during treatment. Patients are required to fast for at least 2 hours before and 1 hour after administration of TAS-120. Patients will be permitted to drink water during this period. Dietary restrictions that limit phosphate intake may reduce the risk of hyperphosphatemia (see [Section 7.8](#)). On non-PK sampling days, TAS-120 can be administered in the morning or evening at the same time (if possible) each day. If a patient misses a dose (i.e., did not take TAS-120 for > 12 hours of the scheduled time of that day), the patient should take the dose on the next day.

8.1.2. Treatment Regimen

TAS-120 will be administered as a daily, continuous, 21-day treatment cycle until at least 1 of the criteria for study discontinuation is met. TAS-120 must be administered as outlined in Study Drug Administration ([Section 8.1.1](#)) and Dose Reduction/Modification Procedures ([Section 8.1.3](#)). There are no breaks in dosing between cycles.

8.1.3. Dose Reduction/Modification Procedures

Dosages will be reduced or modified if AEs are observed according to the criteria described below. In the following sections, AE severity grades are based on the National Cancer Institute (NCI) Common Terminology Criteria for Adverse Events (CTCAE) grade criteria (version 4.03).

8.1.3.1. TAS-120 Dose Reductions for Treatment-emergent Toxicities

Dose reductions must be made according to [Table 5](#). Please note the following:

- A maximum of 2 dose reductions is permitted
- If toxicities requiring further dose reduction recur after the maximum dose reductions have been made, or when dose reduction is not permitted as defined in [Table 5](#) the patient will be discontinued from study treatment.

Table 5: TAS-120 Dose Reduction Levels

1 st Dose Reduction	2 nd Dose Reduction
Dose Reduce to 16 mg	Dose Reduce to 12 mg

If dose modification fails to result in achieving minimal criteria to resume treatment, the investigator should discontinue the patient from study treatment.

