5.5 ≤ P ≤ 7.0 (mg/dL) 1.78 ≤ P ≤ 2.26 (mmol/L)	Grade 2	
 No interruption, implement phosphate binder (monotherapy or in combination) Start with Sevelamer monotherapy (range from 800 mg TID to 2400 mg TID). Re-assess serum phosphate within 7 days, and plan to escalate Sevelamer or add treatment with acetazolamide 250 mg QD or TID and/or lanthanum carbonate 1.0 g QD or TID, and further titration, if phosphate level continues to increase. 	
 Acetazolamide 250 mg QD (and titrate up to BID or TID if required) Lanthanum carbonate (Fosrenol) 1.0 g QD (and titrate up to BID or TID if required)^e
7.0 < P ≤ 10.0 (mg/dL) 2.26 < P ≤ 3.23 (mmol/L)	Grade 3	
 Dose reduce TAS-120 to the next lower dose level and intensify phosphate lowering therapy. If serum phosphorus level has resolved to ≤ Grade 2 within 14 days after dose reduction, continue TAS-120 at the same dose level. If serum phosphorus level not resolved to ≤ Grade 2 after 14 days, further reduce TAS-120 from the last reduced dose level (or no lower than 12 mg) If serum phosphorus level not resolved to ≤ Grade 2 after 14 days of the second dose reduction of TAS-120 (or no lower than 12 mg), dose interrupt TAS-120 until it is resolved to ≤ Grade 2 before resuming TAS-120 at the reduced dose prior to dose interruption. 	
P > 10.0 (mg/dL) P > 3.23 (mmol/L)	Grade 4	Interrupt TAS-120 until serum phosphorus level is resolved to ≤ Grade 2, then resume TAS-120 at the next lower dose level and intensify phosphate lowering therapy. If after 2 dose interruptions and 2 dose reductions, serum phosphorus level is not resolved to ≤ Grade 2 after 14 days, permanently discontinue TAS-120.	

Abbreviations: BID = twice a day; P = Phosphorus; QD = once a day; TID = three times a day; ULN = upper limit of normal

- Serum phosphorus will be tested 4 days (± 24 hours) after Day 1 of Cycle 1 to initiate early intervention for hyperphosphatemia.
- mmol/L = mg/dL x 0.3229 (conversion factor)
- This grading for the range of serum phosphorus levels will be used for the protocol.

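### For a patient already at 12 mg, Table 7 points Grade 4 phosphorus and a new Grade 3 event to a lower dose level that Table 5 does not contain, while Section 8.1.3.1 stops treatment

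*Protocol*

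**What the plan says.** Protocol Section 8.1.1 sets the starting dose: "The dose for TAS-120 is 20 mg QD". Section 8.1.3.1 adds "A maximum of 2 dose reductions is permitted". Table 5 lists 16 mg as the first reduction, and its second and last entry is "Dose Reduce to 12 mg". The same section gives the rule for a patient with no reductions left: "If toxicities requiring further dose reduction recur after the maximum dose reductions have been made, or when dose reduction is not permitted" under Table 5, "the patient will be discontinued from study treatment". No exception is made for hyperphosphatemia. Section 7.3.1 gives as evidence of intolerance "Need for more than the allowed dose reductions of TAS-120 as described in" that section.

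Table 7, in Section 8.1.3.1.1, covers hyperphosphatemia by serum phosphorus.

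- **Grade 3, first step:** go down one level and intensify phosphate-lowering therapy.
- **Grade 3, next step:** reduce again if unresolved after 14 days, with 12 mg as the floor.
- **Grade 3, last step:** if still unresolved 14 days after the second reduction, "dose interrupt TAS-120 until it is resolved to ≤ Grade 2 before resuming TAS-120 at the reduced dose prior to dose interruption".
- **Grade 4:** interrupt until Grade 2 or lower, "then resume TAS-120 at the next lower dose level and intensify phosphate lowering therapy". No floor is stated. Permanent discontinuation follows only if phosphorus is unresolved after 14 days once there have been two interruptions and two reductions.

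The text introducing Table 7 presents it as suggested guidance, subject to the physician's judgment and local practice.

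**The concern.** For a patient who has used both reductions, part of Table 7 cannot be carried out, and its stopping clause does not match the general rule in the same section. One site could stop the patient under Section 8.1.3.1. Another could follow Table 7, find no level to go to, and hold or continue at 12 mg.

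Stopping or continuing affects the data as well as the patient. In the Phase 2 SAP (Section 6.4.2, Table 6), a patient who stops for a reason other than progression or death is censored for PFS at the last tumor assessment (row 5). Progression more than 21 days after the last dose is not counted (note a). DOR, the key secondary objective, uses the same table. The choice also enters the tables of adverse events leading to discontinuation (Section 6.5.2.3) and exposure (Section 6.5.1.1). Hyperphosphatemia is named explicitly among the adverse events of special interest (Section 6.5.2.6).

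**Working it through.** No sample size or error rate is involved. The check follows each provision for a patient at 12 mg, with illustrative phosphorus values.

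**Dose ladder (Sections 8.1.1 and 8.1.3.1, Table 5).** 20 mg, then 16 mg (reduction 1), then 12 mg (reduction 2). Reductions left at 12 mg: 2 − 2 = 0.

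**Grading (Table 7).** 10.5 mg/dL is above 10.0, so Grade 4. 7.5 mg/dL lies between 7.0 and 10.0, so Grade 3. The unit conversion holds: 7.0 × 0.3229 = 2.26 and 10.0 × 0.3229 = 3.23 mmol/L. The problem does not come from the units.

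| Case at 12 mg | Table 7 | Section 8.1.3.1 |
|---|---|---|
| A. 10.5 mg/dL, no earlier interruption, resolves on interruption | Resume one level down; no such level. Stopping clause not met (0 of 2 earlier interruptions) | Further reduction not permitted: stop |
| B. 10.5 mg/dL, both earlier reductions followed Grade 4 interruptions, resolves within 14 days | Resume one level down; no such level. Stopping clause not met, because phosphorus resolved | Further reduction not permitted: stop |
| C. New Grade 3 event, 7.5 mg/dL | First step: go down one level; no such level | Further reduction not permitted: stop |
| D. 7.5 mg/dL, unresolved 14 days after the second reduction | Interrupt, then resume at 12 mg | Stop only if the toxicity is read as requiring a further reduction |

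Cases A to C are direct conflicts. Case B shows that the Grade 4 stopping clause does not close the gap even when its interruption and reduction counts are already met. Case D is different: the last Grade 3 step does not ask for a third reduction, so the trigger in Section 8.1.3.1 is met only on one reading of the toxicity.

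**Text that might settle it.** The paragraph after Table 8 (Section 8.1.3.1.2) covers toxicities handled under Tables 6 to 8. It discontinues a patient who has not recovered within 21 days of the last dose. For one who has recovered, it takes the resumption level from a section cited as 9.1.3.1. Section 9.1 is about tumor tissue pre-screening and has no such subsection. The cited title is that of Section 8.1.3.1. Following the title leads back to Table 5, which has nothing below 12 mg.

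**The case against.** The strongest reply is that the documents already give one answer. Section 8.1.3.1 is mandatory and Table 7 is advisory. The limb about reductions that are not permitted acts as a backstop whenever a table asks for a level that does not exist. Tables 6 and 8 also say to go down one level without repeating the floor, and rely on that backstop. The paragraph after Table 8 sends the resumption dose to the section with that title. The end of Section 8.1.3.1.1 requires discussion with the Medical Monitor when there is doubt about continuing or resuming after a Grade 3 or higher nonhematologic event. Section 7.3.1 allows continued dosing only after case-by-case sponsor review.

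Much of this stands. A reader might infer that the protocol is silent on which text prevails. That goes too far, because the paragraph after Table 8 points toward Section 8.1.3.1. A reader might also infer that Table 7 orders dosing, or that interruption and resumption at 12 mg could cycle unchecked. Table 7 is guidance, and although no count of repeats is set, each hold is bounded by the 21-day limit.

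The reply does not remove the conflict. The pointer carries a wrong section number and sits under the hematologic heading. No sentence says that Section 8.1.3.1 overrides Table 7, which is itself part of Section 8.1.3.1. Section 8.1.2 makes dosing under Section 8.1.3 mandatory, and Section 9.10.2 speaks of phosphorus elevations for which Section 8.1.3.1.1 required action. The Grade 4 row also carries its own stopping clause for a patient who has used both reductions, and that clause stops later than the general rule. The Medical Monitor discussion is triggered by uncertainty; a site that finds either text clear may not see any.

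**Conclusion.** This is an internal inconsistency, and the text is wrong as written. It is firm for Grade 4 phosphorus at 12 mg and for the first Grade 3 step at 12 mg: both call for a level that Table 5 does not contain, while Section 8.1.3.1 stops treatment. It is conditional for persistent Grade 3 phosphorus after the second reduction.

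A reader might infer a three-way contradiction in which Section 8.1.3.1 stops every patient with Grade 3 phosphorus at 12 mg. The documents do not support that, because the last Grade 3 step resumes at the same dose and requires no further reduction. Nor do they support calling hyperphosphatemia the only adverse event of special interest; the Phase 2 SAP names it as one of them.

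The size cannot be stated. The documents do not give the number of patients who reach 12 mg or who then have Grade 3 or 4 phosphorus. Differing practice between sites is a risk, not something shown. The possible effects are on discontinuation, exposure, PFS and DOR data; no effect on the primary ORR is shown. The conclusion assumes that the patient came down from 20 mg by the two Table 5 steps and that no dose increase was agreed with the Medical Monitor.

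**What to change.** The sponsor should reconcile Section 7.3.1, Section 8.1.3.1 with Table 5, the Grade 3 and Grade 4 rows of Table 7, and the paragraph after Table 8. Grade 3 and Grade 4 phosphorus at 12 mg with both reductions used should each have one consistent outcome. The protocol should state whether Section 8.1.3.1 or Table 7 governs hyperphosphatemia, and the reference to Section 9.1.3.1 should be corrected. The choice of rule, including whether any instruction is kept or removed, belongs to the sponsor with the Medical Monitor; this review does not say which dose or rule is right.

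The cost is small: wording changes in these places and a note to sites. No new procedure, visit or data item is needed.
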